7.4.7. Actigraphy

Actigraphy analyses will be described separately.

8. SAFETY ANALYSES

Safety analyses will be conducted using the Safety population.

No inferential comparison of safety endpoints will be performed.

8.1. Extent of Exposure and Treatment Compliance

Total duration of exposure will be calculated in weeks as (the last date study drug administration – the first date study drug administration + 1)/7, regardless of dose interruptions. In addition, duration of exposure accounting for dose interruptions will be calculated as [(last date study drug administration – the first date study drug administration + 1) – sum of (end date of dose interruption – start date of dose interruption + 1)]/7. The dates of interruption are from the Dose Adjustment CRF. Total exposure will be calculated as the total duration of exposure (in days) multiplied by the dose level (mg) during those days. Each duration of exposure and total exposure will be summarized descriptively by treatment for the Safety population. A cumulative summary of the number and percentage of subjects with the following duration of exposure categories will also be provided by treatment (≥ 1 day, ≥ 4 weeks, ≥ 12 weeks, ≥ 24 weeks). In addition, a swim lane figure by treatment will present each subject's time on each dose, accounting for dose interruptions and dose reductions, with the reason for each annotated on the figure.

Randomized treatment compliance during the main study is defined based on the randomized treatment, not accounting for any dose reductions:

Randomized Treatment Compliance (%) = [Total number of randomized dose tablets taken/Total number of randomized dose tablets expected] $\times 100$, where

- Total number of randomized dose tablets taken=Total number of randomized dose tablets dispensed (sum of bottles A, B, C, D from each visit) – Total number of planned dose tablets returned (sum of bottles A, B, C, D from each visit).
- Total number of randomized dose tablets expected= treatment duration $\times 4$ (tablets per day)

where treatment duration is calculated as the number of days between the first dose date and last dose date of study drug, without accounting for any drug interruptions.

Actual treatment compliance during the main study including accounting for any dose reductions or dose interruptions and is defined as:

Actual Treatment Compliance (%) = [Total number of dose tablets taken/Total number of dose tablets expected] $\times 100$, where

- Total number of dose tablets taken=Total number of dose tablets dispensed – Total number of dose tablets returned.

- Total number of dose tablets expected= [dose reduction treatment duration $\times 2$ (tablets per day)] + [treatment duration without reduction or interruption $\times 4$ (tablets per day)]
where dose reduction treatment duration is calculated as the sum from all dose adjustments of the number of days between the dose adjustment start date and dose adjustment end date and the treatment duration without any dose reduction or dose interruption is the sum of these durations number of days from start to end dates.

Dose interruptions resulting drug withdrawal will have a missing end date, and the date of last dose will be used. Subjects who continue into the OLE on a dose reduction may have a missing end date, the day before the first OLE dose will be used.

Treatment compliance will be summarized using descriptive statistics for the Safety population. In addition, the overall treatment compliance will be further categorized as < 80%, 80% – 100% and > 100%, and the number and percentage of subjects with compliance in each category will be presented.

Study drug administration including drug interruptions, dose reductions, overdoses, and study drug dispensing and accountability, calculated durations of exposure, and calculated compliances will be presented in by-subject data listings.

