2.2.2. Study Drug

Study drug is defined as any investigational intervention(s), marketed product(s), or placebo intended to be administered to a study subject according to the study protocol. The IPs to be administered as part of this study are described in [Table 2](#).

Table 2: Study Drug

Treatment Name	300 mg BID*	600 mg BID*	Placebo*
Dose Formulation	Tablet	Tablet	Tablet
Unit Dose Strength(s)	300 mg	300 mg	N/A
Dosage Level(s)	1 x 300 mg tablet + 1 x placebo tablet BID	2 x 300 mg tablets BID	2 x placebo tablets BID
Route of Administration	Oral	Oral	Oral
IP	Rodatristat ethyl	Rodatristat ethyl	Placebo
Packaging and Labeling	IP will be provided in bottles. Each bottle will be labeled as required per country requirement.		

*The components in rodatristat ethyl are provided in Section 3.2.2, Table 1 of the Investigator's Brochure. The active and placebo are formulated with the same excipients.

Abbreviations: BID = twice daily; IP = investigational product; N/A = not applicable

IP will be taken BID with food, approximately 12 hours apart.

Each subject will receive at least 4 bottles (1 kit) of IP at each clinic visit or by mail. There is enough IP in each kit for 4 weeks of dosing, including overage. The bottles of IP given at each clinic visit or by mail should be returned at the subsequent clinic visit for reconciliation and accountability.

The last dose of IP for the Main part of the study will be the last dose the night before the Week 24 visit (all Week 24 assessments will be collected post last dose).

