8.2.2. Overall Summary of Adverse Events

The number and percentage of subjects who experience at least one of the following:

- Any TEAE, All CTCAE grades
- Any TE AESI
- Grade 3+ TEAE
- TEAE by Maximum CTCAE Grade
- Serious TEAE
- TEAE leading to death

- Treatment-related TEAE, All CTCAE grades
- TEAE by highest relationship
- Treatment-related Grade 3+ TEAE
- Treatment-related serious TEAE
- TEAE leading to dose modification
 - TEAE leading to dose reduction
 - TEAE leading to study drug interruption
 - TEAE leading to study drug discontinued
- TEAE leading to discontinuation from the study

As subjects were allowed to dose reduce and hold, this summary will be repeated where the adverse event is assigned to the dose the subject was taking at the time of the adverse event. AEs will be determined to have occurred on a dose (0 mg/placebo, 300 mg, 600 mg) based on the adverse event start date. For example, if the adverse event starts on or after the start of the first dose, before any dose reduction, the adverse event will be counted as occurring during the first dose. If a subject dose reduces (0 mg/placebo or 300 mg) and the adverse event starts after the dose reduction/start of the second dose, the adverse event will be counted as occurring on the second dose. If the AE occurred after the last dose, the AE will be assigned to the last dose taken. The denominator for percentages is the number of subjects who ever took the specified dose.

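### SAP 8.1 total exposure in mg is under-specified: the named duration counts days off drug, and no twice-daily factor is written

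*SAP*

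**What the plan says.** SAP 8.1 defines two durations. The first, total duration of exposure, runs from first to last dose date, "regardless of dose interruptions". The second subtracts interrupted days: "In addition, duration of exposure accounting for dose interruptions will be calculated as" the same span less the summed interruption days. The cumulative-dose rule follows: "Total exposure will be calculated as the total duration of exposure (in days) multiplied by the dose level (mg) during those days". It names the first duration, not the second. Total exposure is then summarised descriptively by treatment in the Safety population.

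Dosing is twice daily (SAP 2.2.2): "IP will be taken BID with food, approximately 12 hours apart". Table 2 gives the dosage level of the 300 mg arm as "1 x 300 mg tablet + 1 x placebo tablet BID" and of the 600 mg arm as "2 x 300 mg tablets BID". When SAP 8.2.2 assigns events to the dose a subject was on, the levels are bare per-intake amounts: "AEs will be determined to have occurred on a dose (0 mg/placebo, 300 mg, 600 mg". In contrast, both compliance formulas in SAP 8.1 write their multipliers (4, or 2 during a reduction) as "tablets per day".

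**The concern.** Two things look wrong when the sentence is programmed as written.

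- **Duration.** The term it uses includes interrupted days by definition, although an interruption-adjusted duration is defined immediately before it.
- **Dose.** The multiplier is in mg, not mg per day. The mg figures the SAP attaches to a dose are what is taken at one intake, and there are two intakes a day.

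At stake is a planned summary of how much drug each arm received. Interruptions need not fall equally across arms: Protocol 4.7 reports dose-dependent gastrointestinal events, and Protocol 4.4.1 and Appendix 2 provide for interruption when they occur. If the higher dose is interrupted more, counting days off flatters that arm's cumulative dose. The SAP's sentence on by-subject listings names durations and compliance but not total exposure, so a wrong total would be harder to spot.

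**Working it through.** The documents state no cumulative-exposure figure, so there is none to reproduce. The check applies the formula to illustrative subjects.

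**Inputs**
- Treatment period: 24 weeks × 7 = 168 dosing days (SAP 2.2). This agrees with a Week 24 target of Day 169 (SAP Table 4) and a last dose the night before that visit (SAP 2.2.2).
- Per-intake dose: 300 or 600 mg, two intakes a day (SAP 2.2.2).
- Days off: 0, 7, 14 and 28. Protocol 8.1.1 allows up to 7 days per temporary discontinuation; 14 and 28 cumulative days are assumptions to show a range.
- Full tablet compliance on all other days: an assumption.

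**Formulas**
- True intake = (168 − days off) × 2 × per-intake mg
- Reading A (named duration, per-intake mg) = 168 × per-intake mg
- Reading B (named duration, daily mg) = 168 × 2 × per-intake mg
- Reading C (per-intake mg, 0 mg on interrupted days) = (168 − days off) × per-intake mg
- Reading D (daily mg, 0 mg on interrupted days) = true intake

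**Results**

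| Days off | True, 300 mg BID | True, 600 mg BID | A ÷ true | B ÷ true | C ÷ true |
|---|---|---|---|---|---|
| 0 | 100,800 mg | 201,600 mg | 0.500 | 1.000 | 0.500 |
| 7 | 96,600 mg | 193,200 mg | 0.522 | 1.043 | 0.500 |
| 14 | 92,400 mg | 184,800 mg | 0.545 | 1.091 | 0.500 |
| 28 | 84,000 mg | 168,000 mg | 0.600 | 1.200 | 0.500 |

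Reading A gives 168 × 300 = 50,400 mg and 168 × 600 = 100,800 mg whatever the days off. For example, at 600 mg BID with 14 days off, 100,800 ÷ 184,800 = 0.545. The interruption effect alone is 168/161 = 1.043 for 7 days and 168/154 = 1.091 for 14.

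**Contrast between active arms.** Without interruptions the 600:300 ratio is 100,800 ÷ 50,400 = 2.00 under A and 201,600 ÷ 100,800 = 2.00 in truth, so the missing factor of 2 cancels. Now suppose every 600 mg subject had 14 days off and no 300 mg subject had any. The true ratio is 184,800 ÷ 100,800 = 1.83, while A and B still report 2.00. Only the interruption error moves the contrast.

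**The case against.** The strongest reply is that the sentence can be programmed correctly as it stands. Dose level is never defined as per intake, and Table 2's dosage-level row carries BID with the amount, so 600 and 1,200 mg a day is a natural choice. The SAP 8.2.2 levels are categories for attributing events, not a definition for this formula. The compliance formulas show that the authors had twice-daily dosing in mind. The closing words of the exposure rule tie the dose to particular days, so an interrupted day could be coded as 0 mg.

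This stands in part. It rules out the stronger reading that a reader might infer, namely that reported exposure will be half the true intake and will also credit days off. The documents do not fix either error, and the two act in opposite directions: exactly half and crediting days off cannot both hold for the same interrupted subject.

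The reply does not make the text sufficient. The duration named is the one defined as ignoring interruptions, with the adjusted one beside it. No place in the SAP gives a daily mg figure as a dose level, although the same section writes a per-day unit for tablets.

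A reader might also infer that interruptions are hidden, or that the safety conclusions depend on this total. Neither is supported. The adjusted duration, the swim lane figure, the adjusted compliance measure and the listings of interruptions all show days off. Adverse events are reported as numbers and percentages of subjects, with no rate per mg, and SAP section 8 plans no inferential safety comparison.

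**Conclusion.** The point holds as a derivation that admits several programmings, the most literal of which is wrong. At 14 days off the readings run from 0.50 to 1.09 of true intake, more than a two-fold spread.

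- If dose level means daily mg, the error is the credited days off: 4% too high for 7 days and 9% for 14.
- If the per-intake labels are used with the named duration, the total is 50% of true intake without interruption and about 55% with 14 days off.

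These sizes assume 168 dosing days and full compliance; the interruption lengths are illustrative, since the documents give no expected frequency. The consequence is confined to the descriptive total-exposure summary. Efficacy, power, type I error and the compliance formulas are untouched. This is a minor correction, worth making because a final SAP should lead two programmers to the same number.

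**What to change.** Replace the total-exposure sentence in SAP 8.1 with wording to this effect: total exposure (mg) is the sum, over dosing intervals defined by the Dose Adjustment CRF dates, of the days in the interval times the total daily mg actually assigned. That daily amount is the per-intake mg × 2 (600 mg a day for 300 mg BID, 1,200 mg a day for 600 mg BID), the actual daily amount of active drug during a reduction, and 0 on interrupted days. Say also that this is assigned exposure and is not adjusted for tablet counts.

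The cost is one sentence and one programming formula. The interruption dates are already used for the adjusted duration, so no new data are needed and no treatment rule changes. If the SAP is not reissued, SAP section 1 allows the change to be documented in the CSR.

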8.2. Adverse Events

Adverse events will be coded using Medical Dictionary for Regulatory Activities (MedDRA) each verbatim term coded to a lower level term (LLT) which is mapped to a preferred term (PT), high level term (HLT), high level group term (HLGT), and a system organ class (SOC). AE severity and intensity using the National Cancer Institute Common Terminology Criteria for Adverse Events (NCI CTCAE, Version 5) are recorded on the eCRF. Both will be presented in listings, CTCAE grade will be used in summaries and analyses.

Adverse event summaries will summarize only treatment-emergent AEs (TEAEs), which are defined as AEs not present prior to the start of study medication, or AEs present before study medication that worsened after starting study medication. If a partially missing date or time of onset allows the possibility that an AE may be a TEAE it will be assumed that it is a TEAE. Each AE will be assigned to the most recent treatment received AEs with a start on or after the first OLE dose will be assigned to the OLE treatment phase and not included in the main study AE analyses. For subjects who discontinued study without going to the open label extension, AEs started after first dose and within the 28 days of last dose will be counted as TEAEs. If it cannot be determined whether an AE is treatment emergent due to a partial onset date, then it will be counted as such. Methodology for imputation of partial AE start and stop dates is described in [Appendix 1](#). Each summary will be displayed by treatment group, including Total Rodatristat ethyl and Overall.

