Study Week¹ (Days)	-4 Wks² (D-28 to D-1) Clinic	D1 Clinic	Wk 2 (D14) Telemed/ Phone Call	Wk 4 (D28) Clinic	Wk 8 (D56) Clinic or Home	Wk 12 (D84) Clinic	Wk 18 (D126) Clinic or Home	Wk 24 (D168) Clinic	Wk 28 (D196) FU ^{3/} ET ^{3,4} Clinic or Home
Vital Signs (BP, HR, RR, temp, oxygen saturation)	X	X		×	×	×	X	X	X
12-Lead ECG ¹²	X	X		×	×	×	×	X	×
Laboratory – Hematology, Coagulation ¹³ , Chemistry, urinalysis,	X	X		×	×	×	×	X	×
Columbia-Suicide Severity Rating Scale (C-SSRS)	X	X		×		×	×	X	X
Hospital Anxiety and Depression Scale (HADS)	X	X		×		×	×	X	X
Quick Inventory of Depressive Symptoms (QIDS-C)	X	X		×		×	×	X	X
Efficacy-Related Assessments									
5 TWM5	X	X		X		X		X	
Right Heart Catheterization (RHC) ¹⁴	X							X	X^{14}
Echocardiography ¹⁵	X					X		X	
WHO FC	X	X		X		X		X	
Plasma NT-proBNP level		×		×		×		×	
PAH Symptoms and Impact Questionnaire (PAH-SYMPACT)		X				×		X	
Actigraphy ¹⁶					\	$X \rightarrow$			
Pharmacokinetics									
Rodatristat PK Sampling ¹⁷		X		X		X		X	
Selexipag PK sampling ¹⁸		X		×					
Pharmacodynamics		Α		Þ		Þ		Α	
Ullile J-HIAA		< >		< >		< >		< >	
Plasma 5-HIAA ¹⁷		X		×		×		X	
Other									
Optional Blood for Future Research Sample		X						X	
Pharmacogenetic Samples		X						X	

Clinical Study Protocol Altavant Sciences GmbH

Visits at Week 2 (Telemed/Phone Call) and Week 4 (clinic visit) can occur within +/-2 days from the randomization date; Visits at Weeks 8 (Telemed/Phone call), 12 (clinic), 18 (clinic or home visit), 24 and 28/Follow Up (clinic) can occur within +/-5 days from the randomization date.

² Screening may be broken up into more than 1 visit, if necessary. Once all screening procedures are complete and the Investigator determines that the patient is eligible, the site must upload/send the required supporting documentation for approval by the Sponsor.

withdraw consent will continue to be followed for vital status from public records such as government vital statistics or obituaries, as allowed by local law, or periodic contact Patients who early terminate from the IP should be asked to return for visits as scheduled for ongoing assessments through the Week 28 Visit. Patients who withdraw consent should be asked to complete the Week 28 Visit for safety. Patients who have not completed the study as planned (through Week 24) cannot participate in OLE. Patients who (about every 6 to 12months).

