6.5.2. Prior and Concomitant Medications

Prior medications are defined as medications that started before first study drug administration and either stopped before or continued after first study drug administration. Concomitant medications are defined as medications that are being taken while on study drug, within 28 days of last dose. Non-PAH concomitant medications are all other concomitant medications not included in the defined of PAH medications above ([Section 6.5.1](#)). Medications that are ongoing on the date of the first administration of study drug will be classified as both prior and concomitant. Any medication that cannot be confirmed as stopping before the start of study drug will be classified as both a prior and a concomitant medication. Imputation of partial dates is defined in [Appendix 1](#).

Prior and non-PAH concomitant medications will be summarized separately and the number and percentage of subjects in each treatment group who took at least one prior (non-PAH concomitant) medication as well as the number and percentage of subjects who took each type of medication will be summarized by Anatomic Therapeutic Class (ATC) Level 2, ATC Level 4, and preferred name for the Safety Analysis Set. If a subject has more than one occurrence of the same preferred name, then the preferred name will be counted only once for that subject. Similarly, if a subject has more than one preferred name within ATC Level 4 or ATC Level 4 within ATC Level 2, then the subject will be counted only once in that ATC Level 4 or ATC Level 2.

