7.4.6. Time to Clinical Improvement (TTCI)

Subjects are considered as having clinical improvement on-treatment during the 24 weeks of the main study if they meet the following criteria:

- 10% increase in 6MWD or 30 meters increase AND
- improvement to WHO FC II or I, or maintenance of WHO FC II
- absence of a deterioration in clinical condition or death (defined as without an adjudicated clinical worsening event during the 24 weeks [see [Section 7.4.2](#)])

On-treatment is defined as randomization date through last dose of study drug + 30 days. TTCI is the number of days from the randomization date to the minimum of (date of the first assessment of 6MWD increase of 10% or 30 meters, first date improved WHO FC, last post-baseline date WHO FC II was maintained from baseline, censor date from an adjudicated TTCW). Subjects who do not improve during the 24 weeks of the main study will be censored at the first OLE dose date if enrolled into OLE or if not enrolled into OLE, the minimum of last dose of study drug + 30 days or date of last contact in the main study.

TTCI will be summarized using the same methods as specified above in [Section 7.4.2](#).

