8.3.1. Treatment Emergent Abnormalities

Quantitative laboratory values will be assigned grades according to the National Cancer Institute (NCI) Common Terminology Criteria for Adverse Events (CTCAE) version 5.0, where applicable.

For each applicable laboratory test, a treatment emergent abnormality will be defined as a post-baseline, through Follow-Up (Week 28) or prior to first dose in the OLE phase, CTCAE grade increase of ≥ 2 grades and any CTCAE grade 3 or 4.

The number and percentage of subjects overall and by laboratory test, with any treatment emergent laboratory abnormality, CTCAE increase of ≥ 2 grades, will be presented.

A separate data listing of treatment emergent Grade 3 and Grade 4 laboratory abnormalities or increase of ≥ 2 grades will also be provided.

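### SAP 6.5.2 and 8.2: the 28-day post-dose windows lack a cut at the first OLE dose for medications and do not clearly cover Week 24 completers who decline the OLE for AEs

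*SAP*

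**What the plan says.** **Medications.** SAP 6.5.2: "Concomitant medications are defined as medications that are being taken while on study drug, within 28 days of last dose". It does not say whether last dose means the last Main Study dose or the last dose overall, and it does not mention the OLE.

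**Adverse events.** SAP 8.2 restricts the AE summaries to treatment-emergent events (TEAEs). Events starting on or after the first OLE dose belong to the OLE. The 28-day limit is introduced by the words "For subjects who discontinued study without going to the open label extension" and reads: "AEs started after first dose and within the 28 days of last dose will be counted as TEAEs". The general TEAE definition in the same section has no upper time limit.

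**Other post-treatment windows in the SAP.**
- Section 8.3.1 takes treatment-emergent laboratory abnormalities "post-baseline, through Follow-Up (Week 28) or prior to first dose in the OLE phase".
- Section 7.4.2 censors adjudicated TTCW at the first OLE dose, or otherwise at the earlier of last dose + 30 days and last contact in the Main Study.
- Section 7.4.6: "On-treatment is defined as randomization date through last dose of study drug + 30 days".
- The visit-window tables in Section 4.7.1 require the assessment to precede the first OLE dose.

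**Schedule.** SAP 2.2.2: "The last dose of IP for the Main part of the study will be the last dose the night before the Week 24 visit". Protocol 1.3 places Week 24 at D168 and the Follow-Up at D196. Its footnote 1 says visits at weeks "24 and 28/Follow Up (clinic) can occur within +/-5 days from the randomization date". The Protocol synopsis also describes the safety follow-up as four weeks after the end of dosing. Protocol 7.9 puts the first OLE dose after all Week 24 assessments, and Protocol 7.7 allows a gap of up to 8 weeks.

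**The concern.** The two 28-day windows do not match the schedule or the SAP's other post-treatment rules.

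For medications, the last Main Study dose is the evening before Week 24 and the OLE can begin at that visit. Without an OLE cut, the 28 days after last dose are then days on open-label active drug. A former placebo patient who starts an antidiarrheal for diarrhea in the OLE would be shown as taking it in the Main Study placebo column, while the diarrhea itself is assigned to the OLE.

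For AEs, the Week 28 visit collects vital signs, ECG, laboratory tests, C-SSRS, HADS and QIDS-C, and a new finding on such a test is often dated to the visit. If the 28-day limit applies to completers who decline the OLE, an on-time visit falls just outside it. If it does not apply, they have no stated limit. Two programmers could produce different TEAE tables from the same data.

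**Working it through.** **1. The plan's own days.** 24 × 7 = 168 and 28 × 7 = 196, as in Protocol 1.3. The SAP numbers first dose as Day 1, so Week 24 is Day 169 (SAP Table 4) and Week 28 is 169 + 28 = Day 197.

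**2. Nominal distance from last dose to Follow-Up.** Last dose = Week 24 day − 1.
- Protocol numbering: 168 − 1 = 167; 196 − 167 = 29 days.
- SAP numbering: 169 − 1 = 168; 197 − 168 = 29 days.

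The nominal visit is one day beyond 28. The duration rule in SAP 4.5 adds one day, giving 30; on that count even a visit exactly 28 days after last dose is day 29.

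**3. Effect of the ±5-day windows.** Distance = 29 + (Week 28 offset) − (Week 24 offset).
- Week 24 on time: 24 to 34 days; 5 of the 11 permitted days are within 28 and 6 are beyond.
- Both visits varying: 11 × 11 = 121 combinations, range 19 to 39 days; 55 are within 28 days and 66 beyond (66/121 = 55%). A last dose + 30 days limit would include 76 of 121.

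These are counts of permitted date combinations, not rates of lost events.

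**4. Medication overlap.** Let g be the days from the Week 24 visit to the OLE start. OLE day k is then g + k days after the last Main Study dose, so the number of OLE days inside the window is max(0, 28 − g).

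| Gap g (days) | OLE days counted as Main Study |
|---|---|
| 0 (immediate rollover) | 28 |
| 7 | 21 |
| 14 | 14 |
| 28 or more | 0 |

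This takes last dose to mean the last Main Study dose. If it means the last dose overall, the overlap is larger.

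**5. The rules side by side.**

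| Rule | Cut at first OLE dose | End for patients not entering the OLE |
|---|---|---|
| Visit windows (4.7.1) | Yes | Upper day of the window |
| Adjudicated TTCW (7.4.2) | Yes | Earlier of last dose + 30 days and last contact |
| AEs (8.2) | Yes | 28 days if study discontinued; completers unclear |
| Laboratory abnormalities (8.3.1) | Yes | Week 28 Follow-Up |
| Concomitant medication (6.5.2) | **No** | 28 days |

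**The case against.** Much can be said on the other side.

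- **Onset, not detection.** A reader might infer that every AE first found at the follow-up visit drops out. The rule turns on when the event started. An event reported at the visit that began by day 28 still counts, and SAP 8.2 resolves partial onset dates toward treatment-emergent. Only a complete onset date beyond day 28 is lost.
- **Not lost from the report.** The AE listings in SAP 8.2.3 are not defined by TEAE status. C-SSRS ideation or behavior in the Main Study is listed separately. HADS, QIDS-C and QTcF are summarized at the maximum post-baseline value. The request in Protocol 9.2.8 to watch for suicidality at the end of treatment is therefore not defeated by the AE window.
- **Not always outside.** The synopsis wording of four weeks after dosing gives day 28, and an early visit falls within the window.
- **Completers not named.** The limit refers to subjects who discontinued the study. Read literally, completers fall under the general definition, which has no end.
- **Medication wording.** Section 6.5.2 also says while on study drug, in a SAP confined to the Main Study. Counting OLE-started drugs is one reading, not an explicit instruction.

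The first three points stand and limit the AE issue. The last two describe ambiguity and do not remove it: the text supports more than one tabulation.

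A reader might also try to estimate affected placebo patients from the 44% incidence of gastrointestinal events in Protocol 4.7. That figure is an AE incidence in healthy subjects at 800 mg BID, a dose not used here, and Protocol 4.7 says most TEAEs resolved without intervention. It is not a rate of drug use, and the number rolling over immediately is unknown.

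**Conclusion.** Both windows need correction, and the effect is modest.

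1. **Medications.** Section 6.5.2 lacks the OLE cut that the comparable rules carry. Followed literally, up to 28 days of open-label medication starts per immediate-rollover patient enter the Main Study table under the original arm. The overlap shrinks with a delayed OLE start and is zero after four weeks.
2. **Adverse events.** Section 8.2 does not settle the position of Week 24 completers who decline the OLE. If the 28-day limit covers them, an AE with a complete onset date on the nominal Week 28 visit is absent from the AE summary tables but present in the listings, and the same laboratory value counts under 8.3.1.

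The number of patients affected cannot be derived from the documents for either part. The two parts concern different patients, OLE entrants and non-entrants, so both effects cannot be at their largest together. Only descriptive tables are touched: SAP Section 8 plans no inferential comparison of safety endpoints, and the efficacy analyses do not use these windows. The documents do not support a claim that a treatment comparison is biased to a known degree.

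**What to change.** **SAP 6.5.2.** For OLE entrants, end the Main Study concomitant-medication window on the day before the first OLE dose. For all others, use the same end date as for TEAEs.

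**SAP 8.2.** For Week 24 completers not entering the OLE, count AEs through the Week 28 Follow-Up visit or last dose + 30 days, whichever is later. For early discontinuers, count AEs through last dose + 30 days, matching the interval in 7.4.2 and 7.4.6.

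The visit-based end should apply to completers only. Footnote 3 of Protocol 1.3 asks patients who stop treatment early to attend through Week 28, while Protocol 8.2.1 says no final follow-up visit is required. Under a visit-based end, someone stopping at Week 4 could have 28 − 4 = 24 weeks of off-drug AEs counted as treatment-emergent. For completers, last dose + 30 days alone is too short, because permitted visits run to day 39.

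**Cost.** A few sentences in the SAP, with no change to study conduct, sample size or the primary analysis. A few events more than 28 days after last dose will count as treatment-emergent. For an OLE entrant with the full 8-week gap, the medication window would run to 56 days after last dose; this matches the AE rule, whose only stated end for OLE entrants is the first OLE dose.
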